12.10. Appendix 10: Abbreviations & Trade Marks

12.10.1. Abbreviations

Abbreviation	Description
AAC	All Analysis Complete
AAUC	Analysis Area Under the Curve
ADAs	Anti-Drug Antibodies
AE	Adverse Event
AIC	Akaike's Information Criteria
ANCOVA	Analysis of Covariance
A&R	Analysis and Reporting
AUC	Area Under the Curve
CDISC	Clinical Data Interchange Standards Consortium
CHDR	Centre for Human Drug Research
CI	Confidence Interval
Crl	Credible Interval
CPM	Conditioned Pain Modulation
CPMS	Clinical Pharmacology Modelling & Simulation
CS	Clinical Statistics
CSR	Clinical Study Report
CTR	Clinical Trial Register
CV _b / CV _w	Coefficient of Variation (Between) / Coefficient of Variation (Within)
DBF	Database Freeze
DBR	Database Release
DOB	Date of Birth
DP	Decimal Places
ECG	Electrocardiogram
eCRF	Electronic Case Record Form
eVAS	Electronic Visual Analogue Scale
EMA	European Medicines Agency
FDA	Food and Drug Administration
FDAAA	Food and Drug Administration Clinical Results Disclosure Requirements
GoF	Goodness-of-Fit
GSK	GlaxoSmithKline
IA	Interim Analysis
ICH	International Conference on Harmonization
IDMC	Independent Data Monitoring Committee
IDS	Integrated Data Standards Library
IMMS	International Modules Management System
IP	Investigational Product
ITT	Intent-To-Treat
LS	Least Squares
mA	Milliamp
MCMC	Markov Chain Monte Carlo
MITT	Modified Intent to Treat

Abbreviation	Description
MMRM	Mixed Model Repeated Measures
OFV	Objective Function Value
PCI	Potential Clinical Importance
PD	Pharmacodynamic
PDMP	Protocol Deviation Management Plan
PK	Pharmacokinetic
PP	Posterior Probability
PopPK	Population PK
QC	Quality Control
QTcF	Frederica's QT Interval Corrected for Heart Rate
QTcB	Bazett's QT Interval Corrected for Heart Rate
RAP	Reporting & Analysis Plan
RAMOS	Randomization & Medication Ordering System
SAC	Statistical Analysis Complete
SAE	Serious Adverse Event
SD	Standard Deviation
SDSP	Study Data Standardization Plan
SE	Standard Error
SEC	Seconds
SOP	Standard Operation Procedure
SP	Study Period
TA	Therapeutic Area
TE	Target Engagement
TFL	Tables, Figures & Listings
UVB	Ultraviolet B

12.10.2. Trademarks

Trademarks of the GlaxoSmithKline Group of Companies	Trademarks not owned by the GlaxoSmithKline Group of Companies
NONE	NONMEM version 7.3 PainCart R / RStudio SAS WinNonLin

12.11. Appendix 11: List of Data Displays

12.11.1. Data Display Numbering

The following numbering will be applied for RAP generated displays:

Section	Tables	Figures
Study Population	1.01 to 1.17	N/A
Pharmacodynamic	2.01 to 2.25	2.01 to 2.09
Safety	3.01 to 3.24	N/A
Pharmacokinetic	4.01 to 4.02	4.01 to 4.03
Pharmacokinetic / Pharmacodynamic	N/A	5.01 to 5.06
Section	Listings	
ICH Listings	1 to 31	
Other Listings	32 to 40	

12.11.2. Mock Example Shell Referencing

Non IDSL specifications will be referenced as indicated and if required example mock-up displays provided in [Appendix 12: Example Mock Shells for Data Displays](#).

Section	Figure	Table	Listing
Study Population		POP_Tn	
Pharmacodynamic	PD_Fn	PD_Tn	PD_Ln
Safety			
Pharmacokinetic			
Pharmacokinetic / Pharmacodynamic	PKPD_Fn		

NOTES:

- Non-Standard displays are indicated in the 'IDSL / Example Shell' or 'Programming Notes' column as '[Non-Standard] + Reference.'

12.11.3. Deliverables

Delivery [Priority] ^[1]	Description
IA 1 SAC [X]	Interim Analysis 1 Statistical Analysis Complete
IA 2 SAC [X]	Interim Analysis 2 Statistical Analysis Complete
SAC [X]	Final Statistical Analysis Complete
AAC [X] ^[2]	Final All Analysis Complete

NOTES:

- Indicates priority (i.e. order) in which displays will be generated for the reporting effort
- The displays listed as Delivery AAC may be delivered for the SAC milestone depending on availability of the displays.

12.11.4. Study Population Tables

Study Population Tables					
No.	Population	IDSL / Example Shell	Title	Programming Notes	Deliverable [Priority]
Subject Disposition					
1.01.	Randomised	ES1xo	Summary of Subject Status and Subject Disposition for the Study Conclusion Record by Relationship to COVID-19 Pandemic	ICH E3, FDAAA, EudraCT Present by: Overall, Related to COVID-19, Not Related to COVID-19	AAC [1]
1.02.	Screened	ES6	Summary of Screen Status and Reasons for Screen Failure	Journal Requirements	AAC [1]
1.03.	ITT	SD1	Summary of Treatment Status and Reasons for Discontinuation of Study Treatment by Relationship to COVID-19 Pandemic	ICH E3 Present by: Overall, Related to COVID-19, Not Related to COVID-19	AAC [1]
1.04.	ITT	ES4	Summary of Subject Disposition at Each Study Period	ICH E3	AAC [1]
1.05.	ITT	ES11	Summary of Outcome of Adverse Events Which Led to Study Withdrawal at Each Study Period	EMA mandated clinical trial results registry	AAC [1]
1.06.	ITT	ES5	Summary of Reason for Withdrawal at Each Period	FDAAA, EMA Only if the withdrawal at each period is collected.	AAC [1]
1.07.	ITT	POP_T1	Summary of Attendance at Each Day		AAC [1]
1.08.	Enrolled	NS1	Summary of Number of Subjects by Country and Site ID Relative to COVID-19 Pandemic Measures	EudraCT/Clinical Operations Present Total column only. Present Overall, and by Before and After implementation of Pandemic Measures	AAC [1]

Study Population Tables					
No.	Population	IDSL / Example Shell	Title	Programming Notes	Deliverable [Priority]
Protocol Deviation					
1.09.	ITT	DV1	Summary of Important Protocol Deviations by relationship to COVID-19 Pandemic	ICH E3 Present only Total column Present by: Overall, Related to COVID-19, Not Related to COVID-19	AAC [1]
Population Analysed					
1.10.	Screened	SP1	Summary of Study Populations	IDSL	AAC [1]
Demographic and Baseline Characteristics					
1.11.	Randomised	DM1xo	Summary of Demographic Characteristics	ICH E3, FDAAA, EudraCT Programming Note: Include BMI summary Present by COVID-19 Pandemic Measures Subgroup: Overall, Before, After	IA 1 [1], IA 2 [2], AAC [3]
1.12.	Enrolled	DM11xo	Summary of Age Ranges	EudraCT	AAC [1]
1.13.	Randomised	DM6xo	Summary of Race and Racial Combinations	ICH E3, FDA, FDAAA, EudraCT	AAC [1]
Medical Conditions					
1.14.	Safety	MH1	Summary of Past Medical Conditions (Cardiovascular Risk Factors)	ICH E3 Present total column only, as per IDSL crossover recommendation.	AAC [1]
1.15.	Safety	MH1	Summary of Current Medical Conditions (Cardiovascular Risk Factors)	ICH E3 Present total column only, as per IDSL crossover recommendation.	AAC [1]

Study Population Tables					
No.	Population	IDSL / Example Shell	Title	Programming Notes	Deliverable [Priority]
Prior and Concomitant Medications					
1.16.	Safety	CM8	Summary of Prior Concomitant Medications	ICH E3	AAC [1]
1.17.	Safety	CM8	Summary of Concomitant Medications by Period	ICH E3 Present by period	AAC [1]

12.11.5. Pharmacodynamic Tables

Pharmacodynamic: Tables					
No.	Population	IDSL / Example Shell	Title	Programming Notes	Deliverable [Priority]
PainCart					
UVB Heat Detection Assessment					
2.01.	UVB-ITT	PD_T1	Summary of UVB Heat Pain Detection (Celsius) on UVB Skin	NVSCATCD=0015 and NVTESTCD=AF001 Programming Note: Repeat for Treatment: GSK3858279; Period: 2 and 3. Geometric Mean and CV (%) Presented for Ratio to Baseline. Day 15 not recorded for UVB heat pain UVB skin assessments	IA 1 [1], IA 2 [2], SAC [3]
2.02.	UVB-MITT	PD_T3	Bayesian Statistical Analysis of Ratio to Baseline Analysis Area Under the Curve (AAUC 1-8 Days) in UVB Heat Pain Detection (Celsius*Day)	Programming note: Include footnotes for the final model fitted, including priors used and interpretations of the direction of effect.	IA 1 [1], IA 2 [2], SAC [3]

Pharmacodynamic: Tables					
No.	Population	IDSL / Example Shell	Title	Programming Notes	Deliverable [Priority]
2.03.	ITT	PD_T1	Summary of UVB Heat Pain Detection (Celsius) on Normal Skin	NVSCATCD=0014 and NVTESTCD=AF001 Programming Note: Repeat for Treatment: GSK3858279; Period: 2 and 3. Geometric Mean and CV (%) Presented for Ratio to Baseline.	AAC [1]
Cold Pressor Assessment					
2.04.	ITT	PD_T1	Summary of Cold Pressor Time to Intolerable Pain Threshold (Seconds)	NVSCATCD=0011 and NVTESTCD=AF004 Programming Note: Repeat for Treatment: GSK3858279; Period: 2 and 3. Geometric Mean and CV (%) Presented for Ratio to Baseline.	IA 1 [1], IA 2 [2], SAC [3]
2.05.	MITT	PD_T3	Bayesian Statistical Analysis of Ratio to Baseline Analysis Area Under the Curve (AAUC 1-15 Days) in Cold Pressor Time to Intolerable Pain Threshold (Seconds*Day)	Programming note: Include footnotes for the final model fitted, including priors used and interpretations of the direction of effect.	IA 1 [1], IA 2 [2], SAC [3]
2.06.	ITT	PD_T1	Summary of Cold Pressor Time to Pain Detection Threshold (Seconds)	NVSCATCD=0011 and NVTESTCD=AF003 Programming Note: Repeat for Treatment: GSK3858279; Period: 2 and 3. Geometric Mean and CV (%) Presented for Ratio to Baseline.	AAC [1]
2.07.	MITT	PD_T3	Bayesian Statistical Analysis of Ratio to Baseline in Cold Pressor Time to Pain Detection Threshold (Seconds) – Area Under Curve	Programming note: Include footnotes for the final model fitted, including priors used and interpretations of the direction of effect.	AAC [1]

Pharmacodynamic: Tables					
No.	Population	IDSL / Example Shell	Title	Programming Notes	Deliverable [Priority]
Electrical Stimulation Assessment					
2.08.	ITT	PD_T1	Summary of Electrical Pain Tolerance Threshold (mA) – Single Stimulus	NVSCATCD=0013 and NVTESTCD=AF004 Programming Note: Repeat for Treatment: GSK3858279; Period: 2 and 3. Geometric Mean and CV (%) Presented for Ratio to Baseline.	IA 1 [1], IA 2 [2], SAC [3]
2.09.	MITT	PD_T3	Bayesian Statistical Analysis of Ratio to Baseline Analysis Area Under the Curve (AAUC 1-15 Days) in Electrical Pain Tolerance Threshold – Single Stimulus (mA*Day)	Programming note: Include footnotes for the final model fitted, including priors used and interpretations of the direction of effect.	IA 1 [1], IA 2 [2], SAC [3]
2.10.	ITT	PD_T1	Summary of Electrical Pain Detection Threshold (mA) – Single Stimulus	NVSCATCD=0013 and NVTESTCD=AF003 Programming Note: Repeat for Treatment: GSK3858279; Period: 2 and 3. Geometric Mean and CV (%) Presented for Ratio to Baseline.	AAC [1]
2.11.	MITT	PD_T3	Bayesian Statistical Analysis of Ratio to Baseline Analysis Area Under the Curve (AAUC 1-15 Days) in Electrical Pain Detection Threshold – Single Stimulus (mA*Day)	Programming note: Include footnotes for the final model fitted, including priors used and interpretations of the direction of effect.	AAC [1]
2.12.	ITT	PD_T1	Summary of Electrical Pain Tolerance Threshold (mA) – Repeat Stimulus	NVSCATCD=0012 and NVTESTCD=AF004 Programming Note: Repeat for Treatment: GSK3858279; Period: 2 and 3. Geometric Mean and CV (%) Presented for Ratio to Baseline.	AAC [1]

Pharmacodynamic: Tables					
No.	Population	IDSL / Example Shell	Title	Programming Notes	Deliverable [Priority]
2.13.	MITT	PD_T3	Bayesian Statistical Analysis of Ratio to Baseline Analysis Area Under the Curve (AAUC 1-15 Days) in Electrical Pain Tolerance Threshold – Repeat Stimulus (mA*Day)	Programming note: Include footnotes for the final model fitted, including priors used and interpretations of the direction of effect.	AAC [1]
2.14.	ITT	PD_T1	Summary of Electrical Pain Detection Threshold (mA) – Repeat Stimulus	NVSCATCD=0012 and NVTESTCD=AF003 Programming Note: Repeat for Treatment: GSK3858279; Period: 2 and 3. Geometric Mean and CV (%) Presented for Ratio to Baseline.	AAC [1]
2.15.	MITT	PD_T3	Bayesian Statistical Analysis of Ratio to Baseline Analysis Area Under the Curve (AAUC 1-15 Days) in Electrical Pain Detection Threshold – Repeat Stimulus (mA*Day)	Programming note: Include footnotes for the final model fitted, including priors used and interpretations of the direction of effect.	AAC [1]
Conditioned Pain Modulation (CPM)					
2.16.	ITT	PD_T1	Summary of Conditioned Pain Modulation Detection Threshold (mA)	Programming Note: Repeat for Treatment: GSK3858279; Period: 2 and 3. Geometric Mean and CV (%) Presented for Ratio to Baseline.	AAC [1]
2.17.	MITT	PD_T3	Bayesian Statistical Analysis of Ratio to Baseline Analysis Area Under the Curve (AAUC 1-15 Days) in Conditioned Pain Modulation Detection Threshold (mA*Day)	Programming note: Include footnotes for the final model fitted, including priors used and interpretations of the direction of effect.	AAC [1]
2.18.	ITT	PD_T1	Summary of Conditioned Pain Modulation Tolerance Threshold (mA)	Programming Note: Repeat for Treatment: GSK3858279; Period: 2 and 3. Geometric Mean and CV (%) Presented for Ratio to Baseline.	AAC [1]

Pharmacodynamic: Tables					
No.	Population	IDS / Example Shell	Title	Programming Notes	Deliverable [Priority]
2.19.	MITT	PD_T3	Bayesian Statistical Analysis of Ratio to Baseline Analysis Area Under the Curve (AAUC 1-15 Days) in Conditioned Pain Modulation Tolerance Threshold (mA*Day)	Programming note: Include footnotes for the final model fitted, including priors used and interpretations of the direction of effect.	AAC [1]
Pressure Pain Assessment					
2.20.	ITT	PD_T1	Summary of Pressure Pain Detection Threshold (kPa)	NVSCATCD=0016 and NVTESTCD=AF003 Programming Note: Repeat for Treatment: GSK3858279; Period: 2 and 3. Geometric Mean and CV (%) Presented for Ratio to Baseline.	AAC [1]
2.21.	ITT	PD_T1	Summary of Pressure Pain Tolerance Threshold (kPa)	NVSCATCD=0016 and NVTESTCD=AF004 Programming Note: Repeat for Treatment: GSK3858279; Period: 2 and 3. Geometric Mean and CV (%) Presented for Ratio to Baseline.	AAC [1]
Serum Concentration					
2.22.	Safety	PD_T5	Summary of Free & Total CCL17 in Serum Concentration-Time Data (pg/mL)	By treatment & study period.	IA 1 [1], AAC [2]
Target Engagement					
2.23.	Safety	PD_T7	Summary of Derived Free and Total CCL17 in Serum Target Engagement Parameters (non-transformed and log-transformed)	By treatment & study period.	IA 1 [1], AAC [2]
2.24.	Safety	PD_T7	Summary of Derived Free and Total CCL17 in Serum Target Engagement Parameters - Percent Reduction and Fold Increase (non-transformed and log-transformed)	By treatment & study period. Include a column Planned Time Point.	IA 1 [1], AAC [2]

Pharmacodynamic: Tables					
No.	Population	IDSL / Example Shell	Title	Programming Notes	Deliverable [Priority]
Immunogenicity					
2.25.	Safety	IMM1	Summary of Immunogenicity	Present by Period. Drop Planned Time Column. Include a Total Column. Footnote: "Note: Percentage is calculated as $(x/n) * 100$ where x = the number of subjects with a positive sample and n = the number of subjects for whom a sample was collected."	AAC [1]

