7.3.1.2. Derived Target Engagement Parameters

All calculations will be based on actual sampling times.

Target engagement parameters listed below will be determined from the observed free CCL17 levels in serum. Additional parameters may be included as required.

Parameter	Parameter description
Cmin	
 Minimum observed concentration Determined directly from the concentration-time data
tmin	
 Time to reach Cmin Determined directly from the concentration-time data
BL	
 Baseline (as defined in Section 5.2)
Percentage reduction	
 Percentage of free CCL17 reduced by the presence of GSK3858279 Calculated by time point as: $(BL - concentration) * 100 / BL$
Maximum Percentage reduction	
 Maximum Percentage of free CCL17 reduced by the presence of GSK3858279 Calculated as: $(BL - Cmin) * 100 / BL$

NOTES:

Additional parameters may be included as required.

Target engagement parameters listed below will be determined from the observed total CCL17 levels in serum. Additional parameters may be included as required.

Parameter	Parameter description
Cmax	
 • Maximum observed concentration • Determined directly from the concentration-time data
tmax	
 • Time to reach Cmax • Determined directly from the concentration-time data
BL	
 • Baseline (as defined in Section 5.2)
Fold increase	
 • Ratio of total CCL17 concentration to baseline • Calculated by time point as: Concentration/BL • Determined directly from the concentration-time data
Maximum Fold increase	
 • Ratio of maximum concentration of total CCL17 to baseline • Calculated as: Cmax/BL • Determined directly from the concentration-time data

NOTES:

Additional parameters may be included as required.

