7.3.2. Statistical Analyses / Methods

Details of the planned displays are provided in [Appendix 12: List of Data Displays](#) and will be based on GSK Data Standards and statistical principles.

Unless otherwise specified, endpoints / variables defined in Section 7.3.1 will be summarised using descriptive statistics by treatment and study period, graphically presented (where appropriate) and listed.

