12.5.4. Reporting Standards for Target Engagement

Target Engagement Concentration Data	
Descriptive Summary Statistics, Graphical Displays and Listings	Refer to IDSL PK Display Standards. Refer to IDSL Statistical Principle 6.06.1. Note: Concentration values will be imputed as per VQD-GUI-000722 (6.0) for descriptive summary statistics/analysis and summarized graphical displays only. NQ values for Free CCL17 will be set to ½ LLQ and subsequent valid concentrations will be retained. Median will be imputed for missing baseline values. LLQ value will be imputed for baseline values equal to zero.

Target Engagement Parameter Derivation	
TE Parameter to be Derived by CPMS	
• None
TE Parameter to be Derived by Programmer	The following TE parameters will be derived by programmer: 
• Cmin, tmin, BL, percentage reduction, maximum percentage reduction for free CCL17• Cmax, tmax, BL, fold increase, maximum fold increase for total CCL17
Target Engagement Parameter Data	
Is NQ impacted PK Parameters Rule Being Followed	Yes, refer to SOP_314000.
Descriptive Summary Statistics, Graphical Displays and Listings	Refer to IDSL PK Display Standards. Refer to VQD-GUI-000722 (6.0).

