12.11.8. Pharmacokinetic Tables

Pharmacokinetic: Tables					
No.	Population	IDSL / Example Shell	Title	Programming Notes	Deliverable [Priority]
Pharmacokinetic Concentrations					
4.01.	PK	PK01	Summary of Serum GSK3858279 Concentration-Time Data (ng/mL)	IDSL. Include 95% Confidence Interval for the mean. Present by period.	IA[1], AAC [2]
4.02.	PK	PK06	Summary of Derived Serum GSK3858279 Pharmacokinetic Parameters (non-transformed and log-transformed)	IDSL. Include Cmax, tmax, tlast, AUC(0-t), AUC(0-7). tmax and tlast should not be log-transformed. Present by period	IA 1 [1], AAC [2]

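### SAP Table 2.24 asks for a log-scale summary of percent reduction in free CCL17, which is often zero or negative on placebo, so the log-scale placebo figure cannot show no change (minor)

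*SAP*

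**What the plan says.** SAP 12.11.5 lists Table 2.24 with a title ending "Percent Reduction and Fold Increase (non-transformed and log-transformed" and the programming note "By treatment & study period. Include a column Planned Time Point". It is due at the first interim and in the final AAC package. Table 2.23 carries the same double scale: "Summary of Derived Free and Total CCL17 in Serum Target Engagement Parameters (non-transformed and log-transformed".

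SAP 7.3.2 confirms that these parameters "will be summarised using descriptive statistics by treatment and study period, graphically presented", so placebo has its own cells.

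SAP 7.3.1.2 computes percentage reduction at each time point as 100 × (BL − C)/BL (in the SAP's notation, opening bracket omitted here, "BL - concentration) * 100 / BL"). Maximum percentage reduction puts Cmin in place of C. Under SAP 5.2, BL is the last pre-dose value of the same period.

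SAP 12.5.4 has rules for non-quantifiable values, missing baselines and zero baselines. It has none for a percent reduction at or below zero. For the PK parameters, by contrast, Table 4.02 in SAP 12.11.8 carries the exemption "tmax and tlast should not be log-transformed". Tables 2.23 and 2.24 carry no such note.

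**The concern.** A log summary suits a positive quantity such as a concentration or a fold increase. Percent reduction is a difference divided by baseline, and on placebo it should scatter around zero. If pre-dose is shown as a time point, it is exactly zero there. A log-scale placebo cell is therefore either undefined or confined to participants whose value happened to fall. In the second case it must show a reduction even where there is none.

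These tables show whether the drug engaged its target. SAP 1.1 records that the study was terminated for not meeting its futility threshold, so the reader of the final report will want to know whether CCL17 was suppressed relative to placebo. The placebo column should not carry an artefact.

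**Working it through.** The plan states no figure on this point, so there is none to reproduce.

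**Inputs.** The formula is from SAP 7.3.1.2 and the period-specific baseline from SAP 5.2. There are five post-dose samples per period (1 h, 3 h, Days 2, 8 and 15; SAP Appendix 2). The sequences are A/P/P and P/A/A (SAP 5.1). Free CCL17 is about 30% of baseline at four weeks (Protocol 4.4). The within-participant CV of free CCL17 is not given; 10% to 50% is assumed. BL and C are taken as independent log-normal with log-scale SD s = √ln(1 + CV²).

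1. **Share at or below zero, Table 2.24, no drift.** BL and C have the same distribution, so P(C ≥ BL) = 1/2 at any CV. Simulation gives 0.50 at CV 10%, 20%, 30% and 50%. With 9 to 15 placebo values at a time point (half of 18 to 30 participants), the chance of at least one such value is at least 1 − 0.5⁹ = 0.998.

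2. **Log summary of what remains.** The simulated geometric mean of the positive reductions, where the true median is 0%, is:

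| CV | 10% | 15% | 20% | 30% | 40% | 50% |
|---|---|---|---|---|---|---|
| Apparent reduction | 7.1% | 10.3% | 13.3% | 18.8% | 23.5% | 27.6% |

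3. **Placebo after active (A/P/P, period 2).** Let the baseline be 30% of the natural level, with log-linear recovery to 100% over the next 28 days. At t days after dosing, ln(C/BL) has mean (t/28) × ln(1/0.3) = (t/28) × 1.204. The share at or below zero is Φ(mean/(s√2)). At CV 20%, s = 0.198 and s√2 = 0.280.
   - Day 8 (t = 7): 0.301/0.280 = 1.07, share 0.86.
   - Day 15 (t = 14): 0.602/0.280 = 2.15, share 0.98.
   - Over CV 10% to 30%: 0.77 to 0.98 on Day 8 and 0.93 to 1.00 on Day 15.
   - With only partial recovery, or a baseline at 70% of the natural level: 0.55 to 0.89 on Day 8 and 0.59 to 0.99 on Day 15.
   
   Some log-scale cells could then rest on very few participants or none.

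4. **Alternatives with no change.** The ratio C/BL is always positive. Its geometric mean is 1, so 100 × (1 − geometric mean of C/BL) = 0% with every value used. The untransformed median is also 0%. The untransformed mean is 100 × (1 − exp(s²)) = −100 × CV², that is −2.25% at CV 15% and −16% at CV 40%. It keeps all values but is pulled slightly negative.

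5. **Table 2.23, maximum percent reduction.** With no change, the lowest of five post-dose values is at or above BL only if BL is the smallest of six, so the share is 1/6 = 16.7%. The untransformed placebo mean is already +10.3%, +18.3%, +24.4% and +32.2% at CV 10%, 20%, 30% and 50%. The apparent reduction there comes mainly from taking a minimum, not from the log.

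**The case against.** The best defence is that the table title is generic. Table 2.24 also covers fold increase, for which a log is proper. Table 4.02 has the same double-scale title and settles exceptions in a note. The PD_T7 shell and the company display standards cited in SAP 12.5.4 cannot be seen and may settle this one. That is fair as to what the programmer would do: the SAP nowhere says that non-positive values are dropped, and omission is only the usual software result. It does not remove the point. The visible text asks for the log summary, and no valid log-scale placebo figure exists whichever way those values are handled.

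The defence is also right that the impact is small. The untransformed summary sits in the same table. Concentrations are in Table 2.22, plots in Figures 2.07 to 2.09, and individual percent reductions in Listing 36. Target engagement is exploratory and descriptive. Protocol 4.4 expects reductions above 90% for a week and 75% at two weeks on drug, so a placebo artefact of 10% to 24% would not hide engagement.

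A reader might go further and infer that the imputation rules create a 50% reduction: "LLQ value will be imputed for baseline values equal to zero", against half that value after dosing. The text does not support this. It reads "NQ values for Free CCL17 will be set to ½ LLQ and subsequent valid concentrations will be retained", with no limit to post-dose samples. On its face a non-quantifiable free CCL17 baseline is also ½ LLQ, and a participant who is unmeasurable throughout shows 0%.

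**Conclusion.** The point holds for percent reduction in Table 2.24 and is minor. The table specifies a log-scale summary by treatment of a quantity that is often zero or negative on placebo, with no visible exemption or handling rule. The share is one half if there is no drift, and probably higher at later time points of placebo periods after active. The apparent placebo reduction of about 10% to 24% assumes no true change, independent log-normal values, a CV of 15% to 40%, and omission of the values that cannot be logged. None of these is stated in the documents.

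Two stronger readings should be avoided. One half is not the share for Table 2.23, where it is about one sixth and where maximum reduction is positive on placebo on either scale. Nor does the fault reach the untransformed summary, the primary PainCart analyses or the futility decision, which Protocol 9.5 ties to cold pressor and electrical tolerance.

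**What to change.** Add a programming note to Table 2.24: summarise percent reduction untransformed only, giving n and the median in each cell. If a log-scale summary is wanted, report 100 × (1 − geometric mean of concentration/BL). Keep the log for fold increase.

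In Table 2.23, exempt maximum percent reduction, tmin and tmax from the log, as Table 4.02 does for tmax and tlast. Add a footnote that maximum reduction is expected to be positive on placebo because it uses the lowest value in the period.

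The cost is two programming notes and a footnote. No new data are needed, and SAP 12.5.4 needs no change on this account.
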